## 9.4 DATA SOURCES

MDV commercial claims database will be used.

Observation period for the primary objective is planned from March 2011 to June 2016 considering the launch date of dabigatran. The observation period for the secondary objective is from March 2008 to June 2016.

## 9.5 STUDY SIZE

This study plans no formal hypothesis testing.

The previous study 1160.279 has identified the patients with confirmed 6 months of baseline period and no OAC treatment (defining “treatment naïve” new starter population). The total of these patients was 62,888. The breakdown by OAC initiated was 7,441 for dabigatran, 23,412 for warfarin, 16,026 for apixaban, 12,779 for rivaroxaban and 3,230 for edoxaban. The average on-treatment follow-up period for pooled OAC in patients with at least one year of baseline period prior to index date excluding the time after switching from one OAC to another was approximately 0.3 year. The average on-treatment follow-up period for pooled

OAC including the time after switching with 6 months of baseline period is unknown, but should be longer than 0.3 year.

## **9.6 DATA MANAGEMENT**

Data are provided as electrical data formatted csv by MDV and stored and managed in Milliman Inc.

SAS and Microsoft Excel are used for statistics.

## **9.7 DATA ANALYSIS**

### **9.7.1 Main analysis**

#### For the primary outcome

Incidence rate of emergency surgery and major bleeding due to fracture/trauma will be described with each number of patients with event, patient-year and 95% confidence interval overall and stratified by age (age <64, 65-74 and >75). Baseline characteristics of patients overall and stratified by age will be provided in a tabulated format.

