## Protocol for non-interventional studies based on existing data

Document Number:	c18071759-01
BI Study Number:	1321-0022
BI Investigational Product(s):	Prazaxa (Dabigatran etexilate)
Title:	Medical Need of Non-vitamin K Oral Anti-coagulant Reversal in Japan: Epidemiological Assessment of Emergency Surgery, Major Bleeding due to Trauma and Fracture, using Large Scale Claims Database
Protocol version identifier:	Version 1.0
Date of last version of protocol:	Not Applicable
PASS:	No
EU PAS register number:	Not Applicable
Active substance:	Dabigatran, warfarin, apixaban, rivaroxaban, edoxaban
Medicinal product:	Dabigatran, warfarin, apixaban, rivaroxaban, edoxaban
Product reference:	Not applicable
Procedure number:	Not Applicable
Joint PASS:	No
Research question and objectives:	The primary objective of this study is to assess, for adult patients initiating an oral anticoagulant for non-valvular atrial fibrillation, the incidence rates of emergency surgery, major bleeding due to fracture, and major bleeding due to trauma, overall and stratified by age (<64, 65-74, >75). The secondary objective of the study is to assess the incidence rates of cardiac tamponade or pericardiocentesis, overall and stratified by age (<64, 65-74, >75). .
Country(-ies) of study:	Japan

Author:	
Marketing authorisation holder(s):	
MAH contact person:	
In case of PASS, add: <EU-QPPV:>	Not Applicable
In case of PASS, add: <Signature of EU-QPPV:>	Not Applicable
Date:	18 July 2017

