## 4. ABSTRACT

Name of company: Boehringer Ingelheim			
Name of finished medicinal product: Prazaxa			
Name of active ingredient: Dabigatran etexilate			
Protocol date: 18 July 2017	Study number: 1321-0022	Version/Revision: 1.0	Version/Revision date: Not applicable
Title of study:  Medical Need of Non-vitamin K Oral Anti-coagulant Reversal in Japan: Epidemiological Assessment of Emergency Surgery, Major Bleeding due to Trauma and Fracture, using Large Scale Claims Database			
Rationale and background:  There has been no epidemiological assessment to investigate the medical need of reversal in patients undergoing emergency surgery or major bleeding from trauma or fracture receiving oral anticoagulant in Japan. The objective of this study is to assess the incidence of emergency surgery and major bleeding associated with fracture and head trauma in Japanese patients prescribed with oral anti-coagulants such as warfarin, dabigatran, apixaban, rivaroxaban and edoxaban			
Research question and objectives:  The primary objective is to assess, for adult patients initiating an oral anticoagulant for non-valvular atrial fibrillation (NVAF), the incidence rates of emergency surgery, major bleeding due to trauma, and major bleeding due to fracture, overall and stratified by age (<64, 65-74, >75). The secondary objective is to estimate the overall and age stratified incidence of cardiac tamponade and pericardiocentesis.			
Study design:  Non-interventional study based on existing health insurance claims data			

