#### Inclusion criteria

1. >18 year old non-valvular atrial fibrillation (NVAF) patients
2. Prescribed dabigatran, rivaroxaban, apixaban, edoxaban or warfarin
3. Patients with confirmed date of initiation of OACs
4. Patients with a minimum of 6 months of enrolment data prior to index date
5. Has an index date between 14th of March 2011 to 30 June, 2016

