#### Exclusion criteria

1. Patients receiving two or more oral anti-coagulants at the same time at index date
2. Patients with prescriptions of index treatment in the 6 months prior to index date
3. Patients without enrolment period of at least six month in the database

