### **9.3.3 Covariates**

These covariates will be used as patient characteristics for the overall population with the primary outcome events.

1. History of stroke or transient ischemic attack yes/no
2. History of myocardial infarction yes/no
3. History of heart failure yes/no
4. History of diabetes mellitus yes/no
5. History of dyslipidemia
6. History of arterial hypertension yes/no
7. History of peripheral artery disease
8. History of kidney impairment
9. History of valvular disease
10. History of liver disease
11. History of dementia
12. History of trauma
13. History of fracture
14. Nursing home resident
15. History of bleeding
16. Charlson co-morbidity index [3]
17. Concomitant medication yes/no for the following:
  - a. aspirin
  - b. clopidogrel
  - c. angiotensin receptor blockers (ARB) or angiotensin converting enzyme inhibitors (ACE)
  - d. beta-blocker
  - e. amiodarone
  - f. calcium-channel blocker (CCB)
  - g. diuretics
  - h. statins
  - i. proton-pump inhibitor
  - j. H2 receptor antagonist

The disease, Charlson co-morbidity index and concomitant medication are defined as [Table 1-Table 4](#). Nursing home resident is defined as MDV codes 113011710, 113016010, 114020910.

Table 1

Definition of clinical history

Disease	Definition	
	ICD10code	prescription
Stroke or transient ischemic attack	I60-I64, G45	-
Myocardial infarction	I21-I23	-
Heart failure	I110, I130, I132, I420, I50	Prescribed furosemide (defined by generic name)
Diabetes mellitus	E100, E101, E109, E110, E111, E119, E14	Prescribed drugs used in diabetes (defined by Anatomical Therapeutic Chemical (ATC) code as A10)
Dyslipidemia	E78	-
Arterial hypertension	I10-I15	Prescribed 2 or more types of anti-hypertensive (defined in Table 2 )
Peripheral artery disease	I702-I709, I71, I739	-
Kidney impairment	N28	-
Valvular disease	I059, I089, I358, I38, I48	-
Liver disease	K70-K77	-
Dementia	F00-F03, G30	-
Trauma	S00-S09, I620, M125, M164, M165, M172, M173, M191, M483, M872, S065, S066, S081, S089, S130, S18, S230, S480, S481, S532, S533, S580, S581, S589, S633, S634, S680, S681, S684, S688, S689, S780, S789, S889, S980, S981, S982, T050, T053, T058, T059, T116, T136, T147, T794, T795, T796, T797, S271, S272, S330, S334, S382, S480, S481, S532, S580, S581, S589, S633, S634, S680, S681	-
Fracture	M484, M80, S02, S12, S22, S32, S42, S52, S62, S72, S82, S92, T02, T08, T10, T12, T142	-

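### The printed age strata leave eligible patients aged 64 and 75 in no stratum, so stratified results coded as written would not sum to the overall figures

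*Combined protocol and SAP*

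**What the plan says.** Section 9.7.1 (For the primary outcome) asks for the rates of emergency surgery and of major bleeding due to fracture or trauma, with "95% confidence interval overall and stratified by age (age <64, 65-74 and >75". The same paragraph uses the age groups a second time: "Baseline characteristics of patients overall and stratified by age will be provided in a tabulated format".

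The same cut-points stand in the Abstract, for the primary objective ("overall and stratified by age (<64, 65-74, >75"), and on the title page, where they apply to the primary objective and also to the secondary one: "incidence rates of cardiac tamponade or pericardiocentesis, overall and stratified by age (<64, 65-74, >75". Section 8 and the data analysis part of the Abstract refer to age stratification without bounds.

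Eligibility under section 9.2 is ">18 year old non-valvular atrial fibrillation (NVAF) patients", with no upper age limit. No exclusion criterion in section 9.2, the Abstract or section 9.11 concerns age. The covariate list in section 9.3.3 does not contain age, and no section says at which date age is determined.

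**The concern.** A stratification has to place every analysed patient in exactly one stratum. The printed bands are strict at the outer ends but closed in the middle, which leaves a one-year gap on each side of the 65-74 band.

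Age-stratified incidence is part of both stated objectives. The study plans no hypothesis test, so these descriptive rates and tables are its product. If the bounds are programmed as printed, patients aged 64 and 75 count in the overall rate but in no age-specific rate or baseline column. If a programmer silently chooses other bounds, the tables will look right but will depart from the written protocol without a record.

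**Working it through.** **Inputs.** Strata <64, 65-74 and >75 (title page, Abstract, section 9.7.1). Eligible age >18, so whole-year ages from 19 upward (section 9.2). For scale only, the previous study's new-starter count from section 9.5: "The total of these patients was 62,888". The breakdown by drug there reproduces it: 7,441 + 23,412 + 16,026 + 12,779 + 3,230 = 62,888.

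**Step 1: is the stratification complete?** Each whole-year age from 19 to 110 was assigned to the bands.

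| Bounds | Ages in no stratum | Ages in two strata |
|---|---|---|
| <64, 65-74, >75 (as printed) | 64 and 75 | none |
| ≤64, 65-74, ≥75 | none | none |
| <65, 65-74, ≥75 | none | none |

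The last two rows are the same rule for age in completed years.

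**Step 2: how many patients could this be?** The protocol gives no age distribution, so two families of distribution were assumed.

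- *Normal*, truncated to 19-111, with age k meaning the interval from k to k+1, means 68 to 78 and SDs 8 to 14 in steps of 1. The unassigned share is P(64) + P(75). The smallest value is 4.64% (mean 78, SD 14): 0.04637 × 62,888 = 2,916 patients. The largest is 7.87% (mean 70, SD 8): 0.07872 × 62,888 = 4,950 patients.
- *Uniform*. Ages 19-100: 2/82 = 2.44%, or 1,534 patients. Ages 60-90: 2/31 = 6.45%, or 4,057 patients.

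**Step 3: what happens to precision in the outer bands?** Let s be the share of the intended band that is lost: age 64 among all ≤64, or age 75 among all ≥75. If events and patient-years scale with patients, the relative width of the interval grows by 1/√(1 − s) − 1. The table uses the normal assumptions.

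| Band | Smallest s | Widening | Largest s | Widening |
|---|---|---|---|---|
| Youngest | 6.7% (mean 68, SD 14) | 3.5% | 23.1% (mean 78, SD 8) | 14.0% |
| Oldest | 4.9% (mean 78, SD 14) | 2.5% | 16.8% (mean 68, SD 8) | 9.7% |

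For example, 1/√(1 − 0.231) − 1 = 14.0%. The two maxima arise under different age distributions and cannot occur together. The 65-74 band is unchanged.

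No loss of patient-years is given, because section 9.5 states that mean follow-up for this population is unknown.

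**The case against.** The strongest objection is that this may not be an error in the plan at all. The protocol text was read from a PDF by a program, no inclusive inequality sign appears anywhere in it, and the adult criterion also reads >18. Lost inequality bars would explain everything, and the three matching printings would not count against that, since all would be affected alike. A 65-74 middle band fits only ≤64 and ≥75, and a competent programmer would probably read it that way. This stands as a possibility, unproven either way, and it is why the source file has to be looked at first.

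It can also be said that section 9.8 provides a second-person code check and two peer reviews, one of which covers consistency of results. Those might catch strata that do not add up. But no sum-to-total check is named, and a checker comparing code with the protocol could pass code that matches the printed bounds.

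Two limits on the size also stand. The percentages rest on assumed age distributions, and 62,888 comes from the previous study, not from a count under this protocol's criteria. The undefined date for age is a separate and smaller gap, worth closing in the same edit.

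**Conclusion.** The concern holds: as printed, the strata are not exhaustive, and exactly two eligible ages, 64 and 75, have no stratum. The section 9.7.1 analysis rule, followed as written, drops them from the age-stratified rates and baseline tables. No other section repairs this.

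The consequence is incompleteness. Overall rates do not change, and each stratum rate remains valid for the ages it contains. Under the assumed distributions, about 2.4% to 7.9% of patients would be unassigned, and under the normal ones the outer-band intervals would widen by about 2.5% to 14%. All of these figures depend on literal coding and on age distributions that the protocol does not supply. The point should be fixed before programming. If the source file shows inclusive signs, the gap disappears and only the date of age remains to be stated.

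**What to change.** 1. Check the source file for the intended inequality signs.
2. State the strata as <65, 65-74 and ≥75 years, with age taken at index date, on the title page (both objectives), in the Abstract and in section 9.7.1.
3. Add to the programming checks in section 9.8 that patients, events and patient-years summed over the three strata equal the overall totals, for each outcome and for the baseline tables.

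The cost is a one-line wording change in three places and one routine check, with no effect on the data extract or the overall analysis. It should be made before programming starts.

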#### For the secondary outcome

2. Incidence rates of cardiac tamponade and peri-cardiocentesis, along with number of events, patient year of follow-up not including time after switch, and 95% confidence interval.

## **9.8 QUALITY CONTROL**

Milliman will conduct a quality check as below:

Calculation check: both of program codes for calculation and the data codes used the calculation will be checked by different person from that who calculated.

Pre-release peer review: comprehensive check on methodology, calculation process, and consistency of results will be performed by a qualified peer-reviewer.

Post-release peer review: comprehensive check on the project will be conducted by qualified peer-reviewer belonging to another office.

## 9.9 LIMITATIONS OF THE RESEARCH METHODS

- The sensitivity and specificity of the definitions used in this study, particularly the use of urgent fee, trauma, fracture MDV codes, is unknown. Additionally, there have been no published studies validating the codes to identify emergency surgery, trauma, fracture, cardiac tamponade or pericardiocentesis.
- The findings from this study may not be generalizable to other Japanese population outside of DPC hospitals
- All information of each patient is from consent giving DPC hospitals. If patients have visits to other medical institutions, these data are not included in the MDV data.

## 9.10 OTHER ASPECTS

None

## 9.11 SUBJECTS

The source population is Japanese patients who have claims data in MDV commercial database. In order to have claims in the database, the patients must have received some medical intervention, out or in-patient hospital visit, or pharmacy prescription from the DPC hospitals in Japan. DPC hospitals are large hospitals, often associated with medical schools or government funding, providing both acute and chronic medical care in Japan. Compared to non-DPC hospitals, they tend to provide more specialized, intensive medical care in addition to outpatient primary care tending to chronic disease requiring non-urgent care. MDV database has contractual agreement to receive claims data from approximately 12% of all DPC hospitals in Japan, and the selection is based on the willingness on the side of DPC hospitals to receive either financial compensation or data services from MDV.

The inclusion and exclusion criteria are intended to select those Japanese atrial fibrillation patients who have non-valvular etiology and have newly initiated oral anti-coagulants for stroke prevention. The exclusion criteria also include patients on dialysis or kidney transplant and having records of deep vein thrombosis or pulmonary embolism to exclude those patients who are presumed to have high risk of bleeding and those receiving OAC for indications other than atrial fibrillation.

The data cut-off of 14 Mar 2011 to 30 June 2016 is to select those claims that have occurred after the launch of dabigatran and to the most recent available data cut from MDV at the time of protocol writing.

The availability of co-variates for matching was evaluated in the feasibility analysis of CTMS 1160.279. External validity was assessed by comparing the incidence of claims defined incidence of stroke, intracranial haemorrhage and systemic embolism in MDV database against previously reported prospective atrial fibrillation registry conducted in Japan by Koretsune et al [4]

### 9.11.1 Cases

Not Applicable

**9.11.2 Controls**

Not Applicable

**9.12 BIAS**

- 1. Selection bias: the database is derived from claims arising from DPC hospitals which tend to treat patients with acute and severe disease, and thus may not reflect the general NVAF population of Japan.
- 2. Misclassification bias: outcomes of emergency surgery and bleeding due to fracture/trauma are not validated.

## **10. PROTECTION OF HUMAN SUBJECTS**

As this is a study based on databases using anonymous and personally unidentifiable data; therefore protection of human subjects is not applicable for this study.

## **11. MANAGEMENT AND REPORTING OF ADVERSE EVENTS/ADVERSE REACTIONS**

No safety reporting is needed as this is a retrospective study using anonymized, existing database.

## **12. PLANS FOR DISSEMINATING AND COMMUNICATING STUDY RESULTS**

A manuscript describing this work will be submitted for publication in a peer-reviewed journal (Japanese medical journal).

**ANNEX 1. LIST OF STAND-ALONE DOCUMENTS**

[figure not shown]
Number	Document Reference Number	Date	Title
	None		

## **ANNEX 2. ENCEPP CECKLIST FOR STUDY PROTOCOLS**

Not applicable

## **ANNEX 3. ADDITIONAL INFORMATION**

None

